11.7 Archiving

The trial documents are to be archived for 15 years. The trial sites will be responsible for archiving their documents (contents of the investigator's file, especially the list of patients, patients' declaration of consent). The IGP will archive the central trial documents, the original CRF (including patient questionnaires, the final report and further reports where necessary).

11.8 End of Trial

11.8.1 Regular / premature end of trial

The **regular end** of the trial is reached when the documentation of the study visits is over for all patients participating in the trial.

The **premature end** of trial can be decided by the principal investigator after the consultation with the scientific advisory board, when recruitment of practices or patients does not meet the recruitment goals, when the number of practices or patients with a premature withdrawal from trial or a permanent violence against the study protocol is expected to avert a successful regular end of trial.

11.8.2 End of trial participation

11.8.2.1 End of trial participation for practices

The **regular end** of the trial participation for a practice is reached when a) the documentation of the study visits is over and b) the treatment in accordance for determined practice status is completed for all patients participating in the trial.

The **premature end** of the trial participation for a practice is reached when the GP withdraws his/her agreement to participate in the trial protocol, or when the principal investigator decides to withdraw a trial site (GP practice) from the trial. Withdrawal has to be done in a written reasoned form. The principal investigator can decide to withdraw a trial site from the trial if:

- It does not satisfy the protocol's technical requirements (e.g. organisational problems in implementing the protocol))
- The implementation of the trial is inadequate for the trial
- The quality of the data is inadequate

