4 STUDY DESIGN

PRIMUM is scheduled as a pragmatic, cluster-randomised controlled trial with the general practice as the unit of randomisation. A clustered design (practices as clusters) was chosen to reduce treatment group contamination, since HCA and GP trained in the intervention will plausible not be able to provide usual care.

Allocation concealment will be disclosed after completion of the baseline documentation for all study patients within a practice but before the intervention begins. Intervention will take place on practice level.

Due to the type of intervention, neither GPs and their patients nor the PRIMUM study team will be blinded to the treatment allocation. However, allocation will neither be revealed to the pharmacologist who is responsible for the MAI rating nor to the study statistician who is responsible for the statistical analyses.

To reduce the contamination of the control group only general information of the treatment in the intervention group is provided in the regular study protocol (a complex intervention including a checklist based pre-consultation interview by the HCA and the use of an internet based CDSS). Detailed information about the intervention treatment is provided only to the intervention group as an appendix to the study protocol in the intervention training.

All primary and secondary outcomes will be measured at patient level at baseline (T0), and at follow-up: 6 months after baseline (T1) and 9 months after baseline (T2).

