11.8.2.2 End of trial participation for patients

The **regular end** of patient's trial participation is reached when documentation of the last planned visit has been completed (T2).

The **premature end** of patient's trial participation is reached

- In cause of death for any reason before the end of trial. If possible, the date and the circumstances of the death (cause of death, location) should be documented.
- In cause of hospitalisation for any reason before the last planned visit has been completed (T2) and before the end of trial.
- In cause of GP decision: The GP can elect to remove a patient from the trial
 - o If following the protocol would represent unacceptable stress for the patient because of his situation (that may have to do with the development of his disease),
 - o If the patient moves to a nursing home and it is technically or organisationally no longer possible to conduct further telephone interviews
 - o If the patient changes to another GP and leaves the trial site.

If the course of events is foreseeable or can be planned a follow-up survey should be brought forward.

- In case of patient's decision: Patients have the right to discontinue the trial without giving reasons at any time and without losing the right to further treatment from the GP. If a patient does not arrive to an appointment, the GP must follow up the case until he has found out why the patient did not turn up. The GP must try to complete and document all the examinations designated in the protocol.

The IGP must be informed of the premature end by fax and will confirm it. In case of a withdrawal, the reasons/circumstances and the most recent status must be documented. If the patient does not withdraw his declaration of consent, his survival status or a hospital stay should be documented at the end of the regular observation period.

[figure not shown]

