12.1 Populations for analysis

The Intention-to-treat (ITT) population will consist of all randomised practices and their patients. Following the ITT principle, practices and their patients will be analysed in the treatment arms to which they were originally randomized, regardless of whether they refused or discontinued treatment, or whether other protocol deviations are known.

The Per-protocol (PP) population will consist of those ITT practices and patients with no major protocol violations. The criteria for the exclusion of practices or patients from the PP population will be determined by the study team at the latest before database lock.

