The statistical analyses of the secondary endpoints will use the same multilevel approach as the primary analysis. All statistical tests will be two-sided at the significance level of $\alpha=0.05$. Because no adjustments for multiple endpoints are planned, findings will be interpreted with caution in view of the number of statistical tests undertaken. Only the result of the primary efficacy analysis will be interpreted in a confirmatory manner. Confirmatory subgroup analyses are not planned. No interim analysis with regard to efficacy will be done.

A complete case analysis will be performed. If any practices or patients are lost to follow-up, analyses will be done replacing the missing follow-up data with the last available or baseline data carried forward for that practice or patient.

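### A randomised practice can be withdrawn for inadequate implementation with no provision that its T1/T2 outcome data are still collected, at odds with the intention-to-treat rules in Sections 11.8.3 and 12.1

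*Protocol*

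**What the plan says.** Section 11.8.2.1 gives a discretionary power: "The principal investigator can decide to withdraw a trial site from the trial if" one of three grounds applies. These are failure to meet technical requirements (organisational problems are the example given), inadequate data quality, and "The implementation of the trial is inadequate for the trial". No threshold is set for any of them. The decision must be written and reasoned. Consultation with the scientific advisory board, which Section 11.8.1 requires before the whole trial is ended early, is not required here.

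Section 4 states that "neither GPs and their patients nor the PRIMUM study team will be blinded to the treatment allocation". Only the pharmacologist who rates the MAI and the statistician are kept blind. Under Section 6 the study team learns a practice's arm once its baseline documentation is complete.

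For patients, Section 11.8.2.2 says "The GP can elect to remove a patient from the trial" on three listed grounds: unacceptable stress, a nursing-home move that rules out telephone interviews, and a change of GP. After a premature end, if consent stands, "his survival status or a hospital stay should be documented at the end of the regular observation period". It adds: "If the course of events is foreseeable or can be planned a follow-up survey should be brought forward".

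Section 11.8.3 treats missing intervention components as a premature end of treatment, after which documentation goes on under the intention-to-treat principle. Section 12.1 analyses all randomised practices and patients as randomised, "regardless of whether they refused or discontinued treatment, or whether other protocol deviations are known". For losses to follow-up, Section 12.2 names a complete-case analysis and also an analysis "replacing the missing follow-up data with the last available or baseline data carried forward for that practice or patient".

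**The concern.** Poor implementation arises after randomisation and depends on the arm. Control practices continue usual care (Section 7.2). Intervention practices must deliver the assistant's checklist interview, the brown-bag review, data entry and checking in AiD+, and the consultation (Appendix B). A rule that lets someone who knows the allocation end a practice's participation for inadequate implementation can therefore act mainly on one arm, and on its weakest performers.

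If follow-up stops at that point, the T1 MAI for about 7 patients per practice is missing for a reason related to the effect being estimated. A complete-case analysis then moves towards the effect among practices that implemented well. Blinding the rater and the statistician does not help, because the selection happens before the data reach them. An SAP can choose how to handle missing values, but it cannot recover medication, diagnosis and symptom data that were never collected.

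**Working it through.** **The plan's own figure.** Section 12.3 assumes d = 0.3, ICC 0.03 and 7 patients per practice, so DEFF = 1 + (7 - 1) × 0.03 = 1.18. With k practices per arm, SE = sqrt(2 × 1.18 / (7k)) in SD units. A two-sample t-test with 2(k - 1) degrees of freedom has power 0.795 at k = 30 and 0.808 at k = 31. The stated 31 practices per arm is reproduced. Recruiting 35 per arm allows for a loss of 4, or 4/35 = 11.4%, from all causes.

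**The rules side by side, for a practice that delivers the intervention badly.**
- Section 11.8.3: treatment ends early for the patients concerned and documentation continues.
- Section 11.8.2.1: the practice's participation may be ended. Its regular end is defined by completed visit documentation and completed treatment, so a premature end most naturally means that the visits are not completed. The section does not say so, and no other section says that T1 and T2 are still documented.
- Section 12.1: the practice stays in the intention-to-treat set either way.
- Section 12.2: if its T1 data are missing, they are dropped or replaced. T1 is the first follow-up visit, so the last available value is normally baseline and the change becomes 0.

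**Size under stated assumptions.** Let w of 35 equal-sized intervention practices be withdrawn and no control practices. Assume an effect of -2.0 (the clinically relevant difference in Section 12.3) in the retained intervention practices and 0 in the withdrawn ones. For carry-forward, take a control change of -0.5, the pilot value in Section 12.3.
- Intention-to-treat effect = -2.0 × (35 - w)/35
- Complete cases = -2.0, so the overstatement factor is 35/(35 - w)
- Baseline carried forward = ((35 - w)/35) × (-2.5) + 0.5

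| w | Intention to treat | Complete cases | Overstatement | Baseline carried forward |
|---|---|---|---|---|
| 2 | -1.89 | -2.00 | 6% | -1.86 |
| 4 | -1.77 | -2.00 | 13% | -1.71 |
| 6 | -1.66 | -2.00 | 21% | -1.57 |

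The carry-forward error is (w/35) × 0.5. At w = 4 it is 0.06 units, or 0.06/1.77 = about 3%, towards no effect.

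**With no true effect.** Suppose the 4 withdrawn practices have a mean change 1, 2 or 3 units worse than the whole arm's mean. The complete-case comparison is then shifted by (4/31) × 1, 2 or 3 = 0.13, 0.26 or 0.39 units. With an SD of 6 and DEFF 1.18, the normal-approximation type I error is 0.055, 0.071 or 0.098.

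**Power is a minor matter.** Losing 4 of 35 intervention practices lowers normal-approximation power at d = 0.3 from 0.864 to 0.842.

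**The case against.** The strongest reply is that the protocol already protects follow-up where it matters. A patient who misses a component falls under Section 11.8.3 and is documented to the end. Section 11.8.2.1 speaks of implementing the trial, not the intervention, and sits beside technical and data-quality grounds that can arise in either arm. Section 12.1 keeps withdrawn practices in the analysis set, Section 12.2 foresees lost practices, and the detail is left to an SAP.

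Much of this stands, and it rules out several stronger readings that a reader might infer.
- *The protocol removes withdrawn practices from the intention-to-treat set.* It does not. Any harm comes through missing data.
- *The protocol says outcome collection stops for a withdrawn practice.* It is silent. The sentence on survival status or a hospital stay concerns patients, and the loss of practice data is an inference. That the principal investigator knows the allocation also follows only from the study team being unblinded.
- *An unblinded GP may remove patients freely.* Removal is limited to three grounds. Two are practical and only unacceptable stress is mainly a matter of judgement. A survey is brought forward when the event is foreseeable.
- *A 13% bias is to be expected.* It requires every withdrawn practice to be an intervention practice with zero effect, and a complete-case primary analysis, which Section 12.2 does not settle. The 10% drop-out allowance covers all causes and does not forecast such withdrawals.

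What the reply does not answer is that inadequate implementation can be handled under either section with opposite consequences for the primary outcome, and that the choice is discretionary and made with the arm known.

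**Conclusion.** The point holds as a conflict between a withdrawal rule and the protocol's intention-to-treat provisions. Sections 11.8.2.1, 11.8.3 and 12.1 must be reconciled, because followed as written the first can lead to arm-dependent loss of the primary outcome. The 6% to 21% overstatement for 2 to 6 withdrawn practices is an upper-end illustration under complete-case analysis. If few practices are withdrawn, or if they differ little from the rest, the bias is small. Under baseline carry-forward with the pilot's control change the error is small and conservative. It is worth correcting in the protocol because uncollected data cannot be restored at the analysis stage. The GP-removal rule is a lesser part of the point, limited to the unacceptable-stress ground.

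**What to change.** Amend Section 11.8.2.1, in parallel with Section 11.8.3, to state that:
- withdrawal of a practice by the principal investigator ends study procedures only;
- T1 and T2 outcome collection continues unless the practice or the patient withdraws consent, covering both the CRF and the telephone interview, whose symptom data the MAI rating uses (Section 8.1.1);
- inadequate implementation is handled by exclusion from the per-protocol set that Section 12.1 already provides, not by withdrawal from follow-up;
- all practice withdrawals are reported by arm with reasons.

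In Section 11.8.2.2, limit the change to removals for unacceptable stress: medication and diagnoses are still documented on the CRF at T1 and T2 where the patient has not withdrawn consent. The other two grounds are left alone, since a practice cannot document a patient who has left it and the nursing-home ground presupposes that interviews are impossible. The grounds for GP removal themselves need not change.

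The cost is protocol wording, some follow-up effort in weak practices, and a few lower-quality CRFs in the primary data. Some MAI ratings after stress-related removal may lack interview symptoms and should be flagged.

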11.8.2.2 End of trial participation for patients

The **regular end** of patient's trial participation is reached when documentation of the last planned visit has been completed (T2).

The **premature end** of patient's trial participation is reached

- In cause of death for any reason before the end of trial. If possible, the date and the circumstances of the death (cause of death, location) should be documented.
- In cause of hospitalisation for any reason before the last planned visit has been completed (T2) and before the end of trial.
- In cause of GP decision: The GP can elect to remove a patient from the trial
 - o If following the protocol would represent unacceptable stress for the patient because of his situation (that may have to do with the development of his disease),
 - o If the patient moves to a nursing home and it is technically or organisationally no longer possible to conduct further telephone interviews
 - o If the patient changes to another GP and leaves the trial site.

If the course of events is foreseeable or can be planned a follow-up survey should be brought forward.

- In case of patient's decision: Patients have the right to discontinue the trial without giving reasons at any time and without losing the right to further treatment from the GP. If a patient does not arrive to an appointment, the GP must follow up the case until he has found out why the patient did not turn up. The GP must try to complete and document all the examinations designated in the protocol.

The IGP must be informed of the premature end by fax and will confirm it. In case of a withdrawal, the reasons/circumstances and the most recent status must be documented. If the patient does not withdraw his declaration of consent, his survival status or a hospital stay should be documented at the end of the regular observation period.

[figure not shown]

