8.1.2 Secondary Outcomes

(1) Change in the appropriateness of prescriptions after 9 months follow-up measured as the difference in the Medication Appropriateness Index (MAI)-Score 9 months from baseline minus baseline (MAI T2–T0): To study late intervention effects a second interval will be measured for the medication appropriateness at T2 (9 months after baseline). Furthermore, treatment effects on each MAI item will be determined.

The following parameters will be determined in order to identify treatment effects on patient related outcomes:

(2) Change in generic health related quality of life measured as the difference in the EQ-5D-Score^{39,40} 6 months from baseline minus baseline (T1–T0) and 9 months from baseline minus baseline (T2–T0): To ascertain whether the intervention improves the generic health related quality of life the EuroQuoL (EQ-5D) will be used.^{39,40} The EQ-5D was feasible in the pilot study and detects even relatively small changes.^{41,42}

(3) Change in functional disability measured as the difference in the VES-13-Score⁴³ 6 months from baseline minus baseline (T1–T0) and 9 months from baseline minus baseline (T2–T0): To ascertain whether the intervention improves functional disability, the activities of daily living will be assessed. In the pilot study the WHO DAS-II was found not to be feasible. In the main study the Vulnerable Elderly Survey, 13 items (VES-13) will be used.⁴³ The VES-13 predicts death and functional decline in vulnerable elderly patients,⁴³⁻⁴⁵ encompasses physical and instrumental activities of daily living and is feasible to use (pers. comm. Dr. [name], geriatrician, VES-13 use in the German PRISCUS-project; pers. comm. [name]: VES-13 use in the Maastricht multimorbidity project).

(4) Change in all cause hospitalisation: To ascertain whether the intervention improves all cause hospitalisation of patients, hospital days are counted irrespectively of reasons for admission.

(5) Change in medication adherence: To determine whether the intervention improves the medication adherence the following outcomes will be measured:

- Change in observed adherence measured as the difference between intake (*patient's interview*) and prescribed medication (CRF reported by physician's) 6 months from baseline minus baseline (T1–T0) and 9 months from baseline minus baseline (T1–T0)

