8.2 Timing of outcome assessment

Study visits: at baseline (T0), 6 months (T1) and 9 months (T2) after baseline. Each time the HCA makes a practice appointment with the patient, and measures body height and weight. Patients fill out a questionnaire in the practice and reply it to the HCA in a closed envelope before leaving. HCA and GP fill out a paper based case report form (CRF). At the end of each visit the HCA sends a control sheet by telefax to the IGP to inform that the visit has taken place. The completed CRF and patient questionnaire are sent by mail to the IGP. Immediately after the receipt of the control sheet trained members of the study team conduct the telephone interview with the patient.

Table 1: Study visits

Month	Before trial begins	0 T0	6 (+/- 1) T1	9 (+/- 1) T2
Visits				
Trial measures for control and intervention group				
Documentation training, GP and HCA	•			
Profile of practices participating in trial	•			
Sociodemographics of GP				
Sociodemographics of HCA	•			
Identification of potentially eligible patients – screening lists	•			
Random lists	•			
Patient registration sheet (In- and exclusion criteria, reasons for non-participation of patients; for included patients with written informed	•			

^a Additional searches should reveal literature, where a direct association between polypharmacy and under-treatment of pain is shown (references are welcome). Otherwise we will get the prevalence of severe pain in our population at baseline.

Month	Before trial begins	0	6 (+/- 1)	9 (+/- 1)
Visits		T0	T1	T2
consent also: name, first name, telephone number, MMSE score)				
CRF, practice documentation				

 Detailed sociodemographics, patient incl. Disease Management Program (DMP) status 		•		

 Patient's current diagnoses 		•	•	•

 Patient's current medication 		•	•	•

 Height and weight of patient 		•	•	•

 Laboratory test results of patient, if available (serum electrolytes K, Na, serum creatinine) 		•	•	•

 Degree of patient's multimorbidity (CIRS) 		•	•	•

 Existing co- and multimorbidity of patient (Charlson Comorbidity Index) 		•	•	•

 Hospital stays (duration, reason) 		•	•	•

 Consultation of specialists 		•	•	•

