12 STATISTICAL CONSIDERATIONS

A detailed description of the statistical methods of this study will be provided in a Statistical Analysis Plan (SAP). Data analysis will be done blinded to treatment arm allocation (i.e. the treatments will be identified as 1 and 2 until analysis is complete). The primary analysis will be based on the 6-month follow-up data (T1).

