
Inequality Tests for Two Means in a Cluster Randomised Trial. Assuming a drop-out rate of approximately 10%, the sample size was adjusted to a total of 70 practices and 490 patients (35 practices and 245 patients in each treatment group).

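### Section 11.8.2.2 ends a patient's participation at any hospitalisation before T2, although hospital days are an outcome and T1 data are needed for the primary endpoint

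*Protocol*

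**What the plan says.** Section 11.8.2.2 sets out when a patient's participation ends early. Next to death stands this entry: "In cause of hospitalisation for any reason before the last planned visit has been completed (T2) and before the end of trial". It has no qualifier on length of stay, urgency or ability to return.

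The same section adds two provisions. A follow-up survey should be moved earlier where events can be foreseen or planned. If consent is not withdrawn, survival status or a hospital stay should be documented at the end of the regular observation period. MAI, EQ-5D, VES-13 and adherence are not named.

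Other sections plan for patients who have been in hospital:
- Section 3 makes all-cause hospitalisation at six and nine months a secondary objective. Section 8.1.2, item (4), defines the outcome: "hospital days are counted irrespectively of reasons for admission".
- Table 1 in section 8.2 schedules hospital stays, with duration and reason, on the practice CRF at T0, T1 and T2. Section 11.3.5 specifies admission and release dates over the last six months.
- Section 12.1 states "The Intention-to-treat (ITT) population will consist of all randomised practices and their patients" and that "practices and their patients will be analysed in the treatment arms to which they were originally randomized".
- Section 12.2 names a complete case analysis and, for those lost to follow-up, carrying forward the last available or baseline value.
- Section 12.3 sizes the trial: "Assuming a drop-out rate of approximately 10%, the sample size was adjusted to a total of 70 practices and 490 patients".

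The primary endpoint is the MAI change from T0 to T1 (sections 8.1.1 and 12.2).

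**The concern.** The protocol uses one event both as an outcome to be counted and as a reason to stop following the patient. Read literally, no patient admitted since baseline attends a regular T1 or T2 visit, so the T1 and T2 hospital-stay fields record no stay since baseline for anyone who does attend. The T0 look-back has no such cut, which distorts the change from baseline.

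For the primary endpoint, the rule creates missing T1 MAI values that could have been avoided. The missingness is triggered after randomisation by an event that section 3 lists among the things the intervention should improve. Neither handling named in section 12.2 recovers the unobserved value, and a larger sample does not cure selection of this kind. The SAP is not at hand, but no analysis plan can restore data that the protocol tells sites not to collect.

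**Working it through.** **1. The plan's own sample size.** Inputs from section 12.3: d = 0.3, two-sided α = 0.05, power 0.80, ICC 0.03, cluster size 7.
- Design effect: 1 + (7 − 1) × 0.03 = 1.18.
- Effective n per arm with k practices: 7k / 1.18. Power is taken from the noncentral t distribution with 2(k − 1) degrees of freedom.
- k = 30 gives 0.795 and k = 31 gives 0.808. So 31 practices per arm (62 practices, 434 patients) is the smallest design reaching 80%, as stated.
- Drop-out: 31 / 0.9 = 34.4, rounded up to 35 per arm, hence 70 practices and 490 patients, as stated.

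The stated sample size is therefore not in error.

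**2. The allowance for loss.** 490 − 434 = 56 patients, and 56 / 490 = 11.4%, for all causes together. If the planned 10% other drop-out occurs, 441 remain, and (441 − 434) / 441 = 1.6% admitted before T1 uses up the rest.

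**3. Which admissions reach which outcome under the rule as written.**
- First admission before T1: no regular T1 or T2 visit. MAI T1–T0 is missing unless a survey was brought forward.
- First admission between T1 and T2: T1 data are already in hand. Only T2 outcomes are lost.

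**4. Scenarios.** The protocol gives no admission rate, so the share h admitted before T1 is assumed.
- Complete cases: 490 × (1 − h), or 490 × (1 − h) × 0.9 with 10% other loss.
- Power: d = 0.3, normal approximation, design effect recomputed for the smaller clusters. On the same basis the planned 434 patients have power 0.82.
- Baseline carried forward: admitted patients get change 0, so a true 2-unit effect becomes 2 × (1 − h), with no other loss.

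| h (assumed) | Complete cases, no other loss | Power | Complete cases, 10% other loss | Power | Carried-forward effect (units) |
|---|---|---|---|---|---|
| 10% | 441 | 0.83 | 397 | 0.80 | 1.8 |
| 20% | 392 | 0.795 | 353 | 0.76 | 1.6 |
| 30% | 343 | 0.75 | 309 | 0.71 | 1.4 |

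The last column belongs to an alternative analysis. It does not add to the loss of complete cases.

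**5. What the table does not measure.** Suppose admitted patients' mean change is g units worse than that of others in both arms, with admission rates h_I and h_C. Then the difference in all randomised patients is the complete-case difference plus g × (h_I − h_C). The protocol gives neither g nor the two rates, so an arm-dependent bias can be described but not sized.

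**The case against.** Several points in the protocol's defence are sound.

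- **Timing.** A reader might infer that any admission before T2 costs the primary outcome. It does not: the primary endpoint is at T1, so only admissions before T1 matter for it.
- **Removal.** A reader might also infer that admitted patients leave the primary analysis. That is literal only for complete cases. Section 12.1 keeps them in the ITT population, and carry-forward gives them a value, usually zero change. The rule weakens the ITT analysis by creating missing data. It does not breach the definition.
- **Mitigation.** The brought-forward survey and the later record of a hospital stay mean that the data are not wholly lost. But the survey needs a foreseeable event, so emergency admissions escape it, and its place after the GP-decision items leaves its scope open. It may also come too early, since section 8.1.1 wants MAI appraised at least three months after the intervention. A record of a hospital stay is not stated to be a full count of days.
- **Section 11.8.3.** Its statement that documentation continues might be read as contradicting the rule. It concerns the end of treatment, not of participation, so there is no direct conflict.
- **Who is lost.** That these are the sickest patients is a plausible inference, not something the protocol says. Planned admissions count too.
- **Practice withdrawal.** Section 11.8.2.1 lets the principal investigator withdraw a practice on the ground "The implementation of the trial is inadequate for the trial". One might infer that this falls mainly on the intervention arm. The wording covers conduct of the trial, which control practices share through recruitment, visits and documentation, and section 12.1 keeps withdrawn practices in ITT. The inference is not supported.
- **Size.** All admission rates are assumed. At 10% with no other loss, 441 still exceeds 434. Power falls more slowly than the patient count because smaller clusters lower the design effect.

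**Conclusion.** The concern holds as an unreconciled contradiction with a real consequence. Section 11.8.2.2 stops follow-up at an event that sections 3, 8.1.2, 8.2 and 11.3.5 treat as outcome data. As written, it makes the T1 MAI missing for patients first admitted before T1, unless a survey was brought forward, and the T2 outcomes missing for those first admitted later.

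The size depends on an admission rate that the protocol does not give. With no other loss, a rate above 11.4% before T1 exhausts the whole drop-out allowance, and power at d = 0.3 drops to just under 80% at about 20%. With the planned 10% other drop-out, about 2% exhausts the allowance, and power is at the 80% margin at about 10%. Under baseline carried forward, a 2-unit effect becomes 1.8 to 1.4 units over the assumed 10% to 30%, given equal rates by arm and the same effect in admitted patients.

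These figures show lost power and dilution. They do not show a bias between arms, which remains possible because the intervention may influence admission.

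**What to change.** Reconcile sections 11.8.2.2, 8.1.2, 8.2 and 12.1 by amendment:
- Delete hospitalisation from the reasons for premature end of patient participation.
- State that an admitted patient stays in outcome follow-up unless consent is withdrawn.
- State that T1 and T2 data are collected at the next possible date, with the actual date recorded.
- State that all hospital days during observation count towards the hospitalisation outcome.

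This concerns data collection only and leaves care to the practice. The cost is a short amendment and some visits outside the ±1 month window. The recorded dates would allow a check of whether late visits affect the result.
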